Laboratory examination	X		X	X	X		X	
Standard electrocardiogram	X		X	X	X	X	X	
Holter					X	X	X	
AFEQT scale	X			X	X	X	X	
Echocardiogram	X		X	X		X	X	
Medication status	X	X	X	X	X	X	X	
Adverse events	X	X	X	X	X	X	X	

Note: m=month; d=day; h=hour.

(1) **V1 Screening period:** If the patient has undergone relevant examinations before signing the informed consent form and within 14 days before surgery, these data can be collected as data for this clinical trial. Patients do not need to undergo relevant examinations, such as laboratory tests, electrocardiograms, etc.

(2) **General information:** date of birth, gender, height, weight.

(3) **Vital signs:** body temperature, blood pressure, heart rate/pulse.

(4) **Medical history:** including hypertension, diabetes, coronary heart disease, stroke, allergies, surgical history, etc.

5) Pregnancy test: urine/blood pregnancy test (only for premenopausal women, only before surgery).

(6) Laboratory examination (V6 only measures NT-proBNP, and all other visits involving laboratory examinations (such as V1, V3 and V4) must complete all the following examination items):

Routine blood test: red blood cells (RBC), white blood cells (WBC), hemoglobin (Hgb), platelets (PLT); Blood biochemistry: alanine aminotransferase/alanine aminotransferase (ALT), aspartate aminotransferase/aspartate aminotransferase (AST), total bilirubin (TBIL), direct bilirubin (DBIL), blood urea nitrogen/urea (BUN/CREA), creatinine (Cr), uric acid (UA); ESR; Electrolytes: potassium ion (K); Coagulation function: prothrombin time (PT), activated partial thromboplastin time (APTT), fibrinogen (FIB); C β -reactive protein; D-dimer; NT-proBNP; myocardial enzyme spectrum and high-sensitive cardiac troponin T: lactate dehydrogenase (LDH), creatine kinase isoenzyme (CK-MB), and high-sensitive cardiac troponin I (hs-cTnI);

(7) Long-term Holter: Use a single-lead 7-day long-term Holter for monitoring.

(8) Medication status: Record the medication used during the study period (from the signing of the informed consent to the end of the follow-up). Routine fluid preparation (normal saline, glucose solution), intraoperative anesthetics, and intraoperative anticoagulants do not need to be recorded. Medication used for corrective treatment of adverse events also needs to be recorded.

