Anticoagulants: Oral anticoagulation should be continued for at least 2 months after catheter ablation. After 2 months, anticoagulation can be selected based on the patient's CHA2DS2-VASc-60 score (see Appendix 14.3), rather than the effect of rhythm control (I, C). Male patients with a CHA2DS2-VASc-60 score of 1 or female patients with a CHA2DS2-VASc-60 score of 2 should consider discontinuing OAC 3 months after ablation, provided that there is no recurrence of atrial fibrillation under strict monitoring. Male patients with a CHA2DS2-VASc-60 score of 2 or female patients with a CHA2DS2-VASc-60 score of 3 without a history of stroke/TIA or systemic embolism should consider discontinuing OAC 3 months after ablation, provided that there is no recurrence of atrial fibrillation under strict monitoring. Male patients with CHA2DS2-VASc-60 score ≥ 3 or female patients with ≥ 4 , or patients with a history of stroke/TIA or systemic embolism, should consider long-term use of OAC after catheter ablation, regardless of whether it is successful or not.

Postoperative anticoagulation therapy monitoring plan

1. NOAC should be the first choice for NOAC/OAC treatment. NOAC has good efficacy and safety, and routine monitoring of coagulation function is not required during use. For patients who have received anticoagulation therapy with NOAC, liver and kidney function should be reviewed regularly and anticoagulation therapy should be adjusted in time.

2. Warfarin

After starting warfarin, INR should be tested once a day. After INR stabilizes, INR should be tested at least once a month to keep INR stable at 2.0~3.0 and TTR $\geq 70\%$.

(4) V4 1 month after surgery

During the follow-up visit $1m \pm 7d$ after surgery, the following information should be collected/completed:

- ◆ Vital signs
- ◆ Laboratory tests
- ◆ Standard electrocardiogram
- ◆ AFEQT quality of life score for patients with atrial fibrillation
- ◆ Cardiac ultrasound

- ◆ Medication status
- ◆ Adverse events & serious adverse events

(5) V6 3 months after surgery

The following information should be collected/completed during the $3m \pm 7d$ follow-up after surgery:

- ◆ Vital signs
- ◆ Laboratory tests
- ◆ Standard electrocardiogram
- ◆ AFEQT quality of life score for patients with atrial fibrillation
- ◆ Cardiac ultrasound
- ◆ Medication status
- ◆ Adverse events & serious adverse events

(6) V7 6 months after surgery

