The following information should be collected/completed at the $6m \pm 15d$ follow-up after surgery:

- ◆ Vital signs
- ◆ Standard electrocardiogram
- ◆ Holter
- ◆ AFEQT quality of life score for patients with atrial fibrillation
- ◆ Cardiac ultrasound
- ◆ Medication status
- ◆ Adverse events & serious adverse events

(7) V8 12 months post-surgery

The following information should be collected/completed at the $12m \pm 15d$ follow-up after surgery:

- ◆ Vital signs
- ◆ Laboratory tests
- ◆ Standard electrocardiogram
- ◆ Holter
- ◆ AFEQT quality of life score for patients with atrial fibrillation
- ◆ Cardiac ultrasound

- ◆ Medication status
- ◆ Adverse events & serious adverse events

Note: Medication status: Record the medication status during the study period (from signing the informed consent to the end of follow-up). Routine solution preparation (normal saline, glucose solution), intraoperative anesthetics, and intraoperative anticoagulants do not need to be recorded. Drugs used for corrective treatment of adverse events also need to be recorded.

Adverse events: Record clinically significant adverse events of the subjects from signing the informed consent to the end of follow-up. Events in which the health status of the subjects does not deteriorate seriously due to planned hospitalization for existing diseases or follow-up required by the protocol are not recorded as serious adverse events.

5. End point

5.1. Primary endpoint:

Change in quality of life at 12 months as measured by the Atrial Fibrillation Quality of Life Survey (AFEQT). Improvement in quality of life from baseline to 12 months after pulsed field ablation procedure or AAD as measured by the Atrial Fibrillation Quality of Life Survey (AFEQT), with values ranging from 20 - 140 (higher scores mean worse outcomes).

5.2 Secondary endpoint:

- (1) The rate of atrial fibrillation-free recurrence during clinical follow-up within 12 months after surgery, that is, the success rate of pulsed field therapy for AF (including atrial tachycardia (AT) lasting more than 30 seconds, atrial flutter (AFL), and AF endpoint events);
- (2) Complications and adverse events during the pulsed field ablation surgery and during the postoperative follow-up, including readmission, cardiovascular events, cardiovascular death, all-cause death, and also including serious adverse events related to the surgery.
- (3) Rehospitalization due to heart failure or recurrence of atrial fibrillation 3 months after surgery;

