- (4) The incidence of AT/AF/AFL events 3 months later.;
- (5) Improvement of cardiac function 6 and 12 months after surgery, including echocardiogram E/e', proBNP, etc.

6. Methods and timing for evaluating, recording and analyzing safety parameters

- (1) Record the occurrence of death, stroke or transient ischemic attack of the subjects during the study;

(2) Surgical operation-related parameters (operation time, left atrial operation time, number of ablation discharges, X-ray exposure time and X-ray radiation, etc.) and intraoperative complications: Observe and record the occurrence of surgery-related adverse events from the beginning to the end of the surgery. All adverse events should be tracked and followed up until they return to normal or baseline, or are sufficient to explain the abnormality. If the subject's participation in this trial ends, it should be tracked until the last follow-up;

(3) Clinically significant vital signs and related examinations:

Vital signs: Vital signs should be checked during the screening period, 1, 2, 3, 6 and 12 months of outpatient follow-up, and observed and recorded;

Laboratory examination: blood routine, blood biochemistry, coagulation function, electrolytes, coagulation function, NT-proBNP, D-dimer, myocardial enzyme spectrum and high-sensitivity cardiac troponin I are performed during the follow-up period. When clinically significant abnormal laboratory test results are found, they should be re-examined and followed up until they return to normal or have no clinical significance or baseline status; relevant laboratory tests need to be completed before the patient is discharged;

Standard electrocardiogram: 12-lead surface electrocardiogram is performed during the screening period, 1, 3, 6 and 12 months of follow-up;

Holter is used for follow-up at 3, 6 and 12 months after surgery.

Echocardiogram: The investigator may choose to perform transthoracic echocardiogram or/and transesophageal echocardiogram according to the patient's condition;

AFEQT Atrial Fibrillation Patient Quality of Life Scale: The patient's quality of life is scored during the screening period and 1, 3, 6 and 12 months after surgery;

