(4) The occurrence of other adverse events and serious adverse events: Observe and record them throughout the trial. Serious adverse events should be tracked until the problem is resolved or the investigator determines that it has become "chronic" or "stable" or "sufficient to explain this abnormality". Reports of these adverse events should be recorded.

7. Safety evaluation

Safety refers to the absence of pulmonary vein stenosis, cardiac tamponade, phrenic nerve injury, esophageal injury, and femoral artery and vein injury, thrombosis/air embolism, myocardial infarction, stroke, TIA, asymptomatic cerebral infarction, coronary artery spasm, vagal reflex with severe bradycardia and other surgical complications during the perioperative period.

8. Time of participation in the study (each participation time and total time)

The time of participation in the study is the time when patients with persistent atrial fibrillation and HFpEF are planned to receive drug treatment or pulsed field ablation surgery, that is, the time of enrollment. The follow-up time is 1 month, 3 months, 6 months, and 12 months after enrollment. The total time is 12 months after the start of treatment. .

9. Data management and statistical analysis plan, data confidentiality plan

(1) The research data are managed and stored in the cardiology laboratory by full-time scientific research personnel.

(2) Data statistics and analysis

1. Statistical processing: SPSS22.0 statistical software was used for statistical analysis.
2. Normally distributed quantitative data, such as troponin, liver and kidney function, blood lipids, height, weight, EF, e/e', proBNP, etc.
3. Non-normally distributed quantitative data, such as age, are described as median ± interquartile range.
4. A t-test is planned for the results of molecular experimental data;
5. The composition ratio is used for statistical description of qualitative data, and the chi-square test is used for statistical inference. Cardiac function (NYHA classification) is tested using the K-W rank sum test;
6. $P < 0.05$ is considered significant.

10. Confidentiality Plan

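### The 6-month NT-proBNP in secondary endpoint (5) is ordered in one place and omitted in two others, under visit labels that conflict; separately, NYHA class is to be tested but no visit lists it

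*Protocol*

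**What the plan says.** **Endpoint.** Section 5.2, item (5): "Improvement of cardiac function 6 and 12 months after surgery, including echocardiogram E/e', proBNP, etc".

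**Flow chart and its note.** The chart places V5 at 3 months, V6 at 6 months and V7 at 12 months. The laboratory row has marks at V1, V3, V4, V5 and V7 and none at V6. Note (6) nevertheless says "V6 only measures NT-proBNP, and all other visits involving laboratory examinations" are to have the full panel.

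**Section 4.3.** The numbering goes from V4 straight to "V6 3 months after surgery", then "V7 6 months after surgery", then V8 at 12 months. The 6-month list, introduced by "The following information should be collected/completed at the $6m \pm 15d$ follow-up after surgery", contains vital signs, ECG, Holter, AFEQT, cardiac ultrasound, medication and adverse events. It contains no laboratory item, whereas the 3-month and 12-month lists both do.

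**Section 6.** NT-proBNP is among the laboratory tests done during follow-up, but no visit is named for them.

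**Section 9.** "Cardiac function (NYHA classification) is tested using the K-W rank sum test". NYHA class is not mentioned in the flow chart, section 3.2, section 4.3 or section 6.

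**The concern.** A named component of a secondary endpoint should be ordered at the visit where it is needed, in every place where a site looks up that visit. Here the 6-month NT-proBNP rests on one footnote. That footnote identifies the visit by a label that means 6 months in the chart and 3 months in section 4.3.

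At stake is the 6-month NT-proBNP comparison in a heart failure population. A sample that is not drawn at its visit cannot be recovered by any later analysis plan. The NYHA point is of the same kind: an analysis is promised for a variable that the schedule does not ask anyone to record, even at baseline.

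**Working it through.** No arithmetic is at issue, so the check sets the two schedules side by side. I take proBNP in endpoint (5) to mean NT-proBNP, the form named in note (6) and section 6.

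**1. Is the flow chart being read correctly?** Table layout can be lost in extraction, so column positions need support. The Holter row reads as V5, V6 and V7, and section 6 gives Holter at 3, 6 and 12 months. The AFEQT row reads as V1 and V4 to V7, and section 6 gives AFEQT at screening and at 1, 3, 6 and 12 months. Both rows agree with the text, so the columns are aligned and the blank laboratory cell does fall at 6 months. The section 4.3 list, which is not a table, shows the same omission.

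**2. Visit labels.**

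| Time | Flow chart | Section 4.3 |
|---|---|---|
| 1 month | V4 | V4 |
| 3 months | V5 | V6 |
| 6 months | V6 | V7 |
| 12 months | V7 | V8 |

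**3. Coverage of the measurements involved.**

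| Measurement | Flow chart row | Note (6) | Section 4.3 list | Status |
|---|---|---|---|---|
| E/e', 6 months | yes | – | yes | consistent |
| E/e', 12 months | yes | – | yes | consistent |
| NT-proBNP, 12 months | yes | full panel | yes | consistent |
| NT-proBNP, 6 months | blank | yes, as V6 | no | contradictory |
| NYHA class, any visit | no | no | no | not listed |

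Of the four combinations named in endpoint (5), 4 − 1 = 3 are consistently ordered and one is not. NYHA is in the table because section 9 tests it; endpoint (5) does not name it.

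**4. What a site would do under each reading.**

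- Flow chart with its note: NT-proBNP is drawn at 6 months, provided the note is read despite the blank cell.
- Section 4.3 alone: full laboratory tests at 3 months, none at 6 months. The 6-month NT-proBNP is lost.
- Note (6) applied with section 4.3 numbering: the note points to the 3-month visit, so that panel shrinks to NT-proBNP and nothing is drawn at 6 months.

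The last two are different readings, and one site would not follow both. Each loses the 6-month sample.

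**5. Other differences between the same two schedules.** At 3 months the chart has Holter and no echocardiogram, while section 4.3 has cardiac ultrasound and no Holter. The windows at 6 and 12 months are ±7 days in the chart and ±15 days in section 4.3. These do not bear on the NT-proBNP point, but they show that the two schedules have not been reconciled.

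**The case against.** The strongest reply is that the protocol does order the sample. Note (6) belongs to the flow chart, V6 is 6 months there, and the intention is plain. Section 4.3 prints the month beside each visit number and skips V5, so its labels look like a numbering slip that a careful coordinator would see through. Section 6 also expects NT-proBNP during follow-up. The primary endpoint is not involved, since AFEQT is ordered at screening and at 12 months in both places.

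The reply is right about intent and about the limited reach of the problem. It does not remove the contradiction: the chart's own cell and the section 4.3 list both omit the sample, and section 6 names no visit.

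Several stronger readings are tempting, and the protocol does not support them:

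- *The cardiac-function endpoint cannot be delivered, or loses its 6-month timepoint.* E/e' at 6 months is ordered in both schedules, and note (6) does order NT-proBNP then.
- *Missing values would line up with treatment through centre.* The protocol does not say how the drug and ablation groups are spread over centres, so this is conjecture.
- *NYHA will be missing for everyone.* The case report form is not shown. What can be said is that no visit lists NYHA.
- *NYHA is part of endpoint (5).* The endpoint ends with an open-ended term but does not name NYHA. It is a section 9 analysis variable.

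**Conclusion.** The point holds as an internal inconsistency of moderate weight. One of the four named measurement-by-time combinations in secondary endpoint (5), NT-proBNP at 6 months, is scheduled contradictorily; the other three are sound. At a site that follows section 4.3 literally, none of the 6-month NT-proBNP values would be collected. The protocol does not say which schedule sites will use or how patients are distributed among them, so the overall loss could lie anywhere from 0 to 100% of these values.

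Separately, the planned Kruskal-Wallis test of NYHA class has no listed point of collection. The primary endpoint is unaffected. The conclusion assumes that proBNP means NT-proBNP and that the chart columns are aligned as checked above.

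**What to change.** 1. Use one visit numbering in the flow chart, its notes and section 4.3, for example V5, V6 and V7 for 3, 6 and 12 months.
2. Mark the 6-month laboratory cell in the flow chart as NT-proBNP only, and add NT-proBNP to the 6-month list in section 4.3.
3. Either add NYHA class to the baseline, 6-month and 12-month visits, or delete the NYHA test from section 9.
4. In the same edit, reconcile the 3-month Holter and echocardiogram entries and the 6- and 12-month visit windows between the two schedules.

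The cost is small: text corrections in two places and, if NYHA is kept, one item on the case report form. Note (6) already intends the 6-month blood sample, so it adds no new assessment. The correction should reach sites before patients arrive at their 6-month visits, because a missed sample cannot be replaced afterwards.

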2.1 Research objectives

This study aims to evaluate the mid- and long-term clinical efficacy and safety of pulsed field ablation in the treatment of patients with persistent atrial fibrillation and HFpEF by recording and analyzing the differences between the effects of pulsed field ablation and drug therapy in patients with persistent atrial fibrillation and HFpEF. At the same time, the risk factors affecting the outcome of atrial fibrillation ablation, postoperative recurrence, and improvement of cardiac function were analyzed to better guide the application of pulsed field catheter ablation in persistent atrial fibrillation and HFpEF, and also to provide some theoretical basis and clinical evidence for the treatment strategy of patients with atrial fibrillation and HFpEF.

2.2 Research content

This study is a prospective, multicenter cohort study.

- (1) To observe the perioperative safety of pulsed field catheter ablation for patients with persistent atrial fibrillation and HFpEF;
- (2) To observe the improvement of cardiac function, the treatment effect and recurrence rate of atrial fibrillation in the pulsed field ablation group compared with the drug treatment group 1 month, 3 months, 6 months and 12 months after surgery;
- (3) To study the treatment strategy during the pulsed field ablation procedure, such as the correlation between ablation time, ablation site and the recurrence of atrial fibrillation and cardiac function after surgery, so as to guide better cryoablation strategies.

3. Study population

This study selected patients with persistent AF and HFpEF and divided them into a drug group (treated with class I or class III antiarrhythmic drugs) and a surgical group (Medtronic Pulse Select pulsed field ablation).

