The Safety and Efficacy of Pulsed Field Ablation for Patients with Persistent Atrial Fibrillation Comorbid with HFpEF: a prospective, multicenter cohort study

Protocol Version and Date	V1.0. 20250425
Clinical Research Unit	Affiliated Hospital of Nantong University
Principal Investigator	[name]
Sponsor	Affiliated Hospital of Nantong University

Study plan

Project name	The Safety and Efficacy of Pulsed Field Ablation for Patients with Persistent Atrial Fibrillation Comorbid with HFpEF: a prospective, multicenter cohort study		
Project source	Jiangsu Provincial Research Hospital: YJXYY202204-YSB59		
Main investigator	[name]	Contact	[name]
Funding source	Hospital multi-center clinical research project	Funding received	100,000

Study Protocol Summary

Study number	2025-K119-01
Study name	The Safety and Efficacy of Pulsed Field Ablation for Patients with Persistent Atrial Fibrillation Comorbid with HFpEF: a prospective, multicenter cohort study
Study purpose	To evaluate the difference between pulsed field ablation and medical therapy in patients with persistent atrial fibrillation and HFpEF
Study design	Prospective, multicenter cohort study
Study equipment	Medtronic Pulse Select Pulsed Field Ablation
Sample size	158

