	
Life Survey (AFEQT), with values ranging from 20 - 140 (higher scores mean worse outcomes).
 
Secondary End Points
 
(1) The rate of atrial fibrillation-free recurrence during clinical follow-up within 12 months after surgery, that is, the success rate of pulsed field therapy for AF (including atrial tachycardia (AT) lasting more than 30 seconds, atrial flutter (AFL), and AF endpoint events);
 
(2) Complications and adverse events during the pulsed field ablation surgery and during the postoperative follow-up, including readmission, cardiovascular events, cardiovascular death, all-cause death, and also including serious adverse events related to the surgery.
 
(3) Rehospitalization due to heart failure or recurrence of atrial fibrillation 3 months after surgery;
 
(4) The incidence of AT/AF/AFL events 3 months later.;
 
(5) Improvement of cardiac function 6 and 12 months after surgery, including echocardiogram E/e', proBNP, etc.

Statistical analysis
	
OPC was analyzed based on previous clinical research data and used for comparison and evaluation of the main evaluation indicators. According to the current literature on the treatment of drug-refractory atrial fibrillation, the main evaluation indicator comparison target value was 80%.
 
1. Completion status and demographic analysis
 
Summarize the number of enrollments and completions of each center, and list the list of dropouts. Make a detailed list of the size of different data sets in each group, the distribution of cases in each center, the comparison of the total dropout rate, and the reasons for non-completion. Describe, analyze and evaluate the patient's demographic characteristics (age, gender, etc.), relevant medical history, treatment history, etc.
 
2. Safety evaluation
 
List the number and frequency of all adverse events, as well as the incidence of adverse events and serious adverse events. Make a cross-tabulation description of the changes in laboratory indicators before and after. The exact probability

	method was used to compare the two groups of adverse events.
--	--

Flow chart

Name	Screening period		Treatment period		Follow-up period			
	V1	V2	V3	V4	V5	V6	V7	
Visit point								
Visit time	-14d ~ 0d	0 d (Operation)	1-7 d (Before discharge)	1m ± 7d	3m ± 7d	6m ± 7d	12m ± 7d	
Informed consent	X							
General information	X							
Vital signs	X		X	X	X	X	X	
Medical history	X							
Inclusion criteria	X							

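### No confounding control is stated for the non-randomised PFA-versus-drug comparison of AFEQT, and the only test linked to AFEQT is an unadjusted t-test used for sizing

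*Protocol*

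**What the plan says.** **Design.** Section 2.2 calls the study a prospective multicentre cohort. Under section 3 (Study population), patients are "divided them into a drug group (treated with class I or class III antiarrhythmic drugs) and a surgical group" treated with PFA. Section 8 sets the start of participation at the point when patients "are planned to receive drug treatment or pulsed field ablation surgery, that is, the time of enrollment". The protocol shown mentions no randomisation, matching or rule for who enters which group.

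**Purpose.** The synopsis gives it as "To evaluate the difference between pulsed field ablation and medical therapy in patients with persistent atrial fibrillation and HFpEF". Section 2.1 speaks of "recording and analyzing the differences between the effects of pulsed field ablation and drug therapy", and section 2.2, item 2, adds cardiac function and the "recurrence rate of atrial fibrillation in the pulsed field ablation group compared with the drug treatment group". The primary endpoint (section 5.1) is AFEQT change from baseline to 12 months.

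**Analysis.**
- Section 9, whose title includes a statistical analysis plan, does not mention AFEQT. Its item 4 reads "A t-test is planned for the results of molecular experimental data". Its item 5 reads "The composition ratio is used for statistical description of qualitative data, and the chi-square test is used for statistical inference", followed by a Kruskal-Wallis test for NYHA class.
- The synopsis gives an objective performance criterion of 80% for the main indicator and an exact test comparing the groups on adverse events. It also describes and evaluates "demographic characteristics (age, gender, etc.), relevant medical history, treatment history, etc".
- Section 3.1 sizes the study with an unequal-variance two-sample t-test of AFEQT scores.

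**The concern.** When treatment is not assigned at random, patients who receive PFA may differ from those given drugs in age, AF duration, atrial size, natriuretic peptide level or starting quality of life. Any such difference that predicts AFEQT enters an unadjusted comparison as if it were a treatment effect. The shared entry criteria narrow the differences but still allow, for example, AF duration up to 3 years and left atrial diameter up to 50 mm.

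Whether confounding is controlled, and how, decides what the primary result means, so it should be fixed before outcomes are seen. Here the methods that are written down point away from adjustment: an unadjusted t-test behind the sample size, unadjusted tests in section 9, and a comparison with a fixed target in the synopsis.

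**Working it through.** **1. Tests named in the protocol, set against the primary comparison**

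| Place | Method | Applied to | Adjusted? |
|---|---|---|---|
| Section 3.1 | Two-sample t-test | AFEQT score, for sizing | No |
| Section 9, item 4 | t-test | Molecular data (not a listed endpoint) | No |
| Section 9, item 5 | Chi-square | Qualitative data | No |
| Section 9, item 5 | Kruskal-Wallis | NYHA class | No |
| Synopsis | 80% target value | Main indicator | Not a two-group comparison |
| Synopsis | Exact test | Adverse events, two groups | No |

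No regression, matching, weighting, stratification or propensity score appears for the treatment comparison.

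**2. The plan's own figure.** Inputs from section 3.1: means 80.6 and 70.6, SD 19.8 in both groups, two-sided 5%, 63 per group.
- Standard error = 19.8 × √(2/63) = 3.528.
- Noncentrality = 10/3.528 = 2.835, with 124 degrees of freedom and critical value 1.979.
- Power = 0.803, matching the stated 0.80306. Then 63/0.8 = 78.75, so 79 per group and 158 in total.

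The arithmetic is right. It makes no allowance for non-random group formation, and it compares 12-month scores although the endpoint is change.

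**3. What an imbalance could do to that t-test (illustration).** Assume no true effect and a shift of *b* points carried fully into the 12-month comparison. The noncentrality is *b*/3.528. At 63 per group:

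| *b* | Noncentrality | Type I error |
|---|---|---|
| 2 | 0.567 | 8.7% |
| 3 | 0.850 | 13.5% |
| 5 | 1.417 | 29.0% |

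The 5-point value is the baseline gap (71.3 versus 76.3) in one ablation-versus-drug cohort that section 3.1 cites. It comes from a different population, and full carry-over to 12 months is an assumption.

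**4. Handling of baseline AFEQT.** Take a 5-point baseline gap, SD 19.8 at both times, 63 per group, and an assumed baseline-to-12-month correlation r = 0.3/0.5/0.7.
- *If both groups share one regression line:* the unadjusted change score is biased by (1 − r) × 5 = 3.5/2.5/1.5 points, with SD 19.8 × √(2(1 − r)) = 23.4/19.8/15.3. Type I error is 13.2%/10.8%/8.5%.
- *If the gap is stable over time:* the change score is unbiased, but adjustment for baseline AFEQT alone is biased by −(1 − r) × 5, with SD 19.8 × √(1 − r²). Type I error is 17.8%/12.8%/9.1%.

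Neither handling is safe in both situations, which is the reason for a paired sensitivity analysis.

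**5. Cost in power.** For the adjusted model, SD = 19.8 × √((1 − r²) × V), where V is the variance inflation from covariates related to group (assumed). At r = 0.3 and V = 1.25, SD = 21.12, standard error = 3.763, noncentrality = 2.658 and power = 75%. At r = 0.5 and 0.7 with the same V, power is 83% and 94%. For 80% power at V = 1.25, 71/59/41 evaluable per group are needed, or 89/74/52 enrolled with 20% dropout, against 79 planned.

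**The case against.** **A separate analysis plan may supply the adjustment.** This is the best defence, and it covers detail such as the covariate list and how centre is handled. It does not cover the core. Section 9 presents itself as the analysis plan and makes choices, and the sample size rests on an unadjusted test. A later document would have to add the primary analysis and depart from the method used for sizing.

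**Three stronger readings are tempting but not supported.**
- A reader might infer that groups are formed by planned treatment. Section 8 defines when participation starts, not how patients are allocated; the text supports only that no allocation rule is stated.
- A reader might infer that every test in section 9 is an unadjusted comparison of PFA with drugs. Section 9 does not say what its t-test, chi-square and Kruskal-Wallis tests compare. Only the sizing t-tests and the exact test for adverse events are explicitly two-group.
- A reader might infer that the result will be biased in favour of PFA, or by a known amount. Nothing in the protocol fixes the direction or size.

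**The numbers alone do not prove the case.** This stands. They rest on an assumed gap and assumed correlations. The change-score calculation concerns a test that the protocol never names, and it does not show baseline adjustment to be better in all situations. The case for adjustment rests on design.

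**Section 2.1 plans an analysis of risk factors.** It does, but with no method and no link to the treatment comparison.

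**Conclusion.** The concern holds as a matter of design: a non-randomised comparison is the study's stated purpose, and no control of confounding is stated for it. The synopsis adds a conflict, because its only stated analysis of the main indicator is an 80% target value, while the objective is a difference between two groups.

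The size and direction of the bias are unknown. The figure of about 29% type I error shows what a fully carried 5-point imbalance would do at 63 per group; it is not a forecast, and a 2-point imbalance gives about 9%. The 63 and 79 per group are correctly computed for the unadjusted test. Two-sided type I error does not depend on which direction of the AFEQT scale is favourable.

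This must be fixed before data are seen, since the primary result could not otherwise be read as an effect of treatment.

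**What to change.** 1. State in section 9 that the primary analysis is the PFA-versus-drug comparison of AFEQT change at 12 months, adjusted by regression for baseline AFEQT and a short prespecified list of screening variables (for example age, sex, AF duration, left atrial diameter, LVEF and NT-proBNP), or by one named propensity-score method. In a regression with baseline in the model, the group coefficient is the same for change and for 12-month score, so the section 5.1 endpoint is kept.
2. Prespecify one sensitivity analysis: the change score adjusted for the same other variables but not for baseline AFEQT. Any discrepancy then reflects the handling of baseline alone.
3. Replace the 80% target-value statement in the synopsis, or reconcile it with the two-group primary analysis.
4. Restate the power of 63 evaluable per group for the adjusted analysis, with the assumed correlation and variance inflation written down.

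**Cost.** Protocol wording and modest programming. AF duration must become a recorded data item, though exclusion criterion 1 already requires it to be ascertained; the other example variables are collected at screening. Some precision may be lost, and under the less favourable assumptions above more than 79 per group would be needed. Adjustment does not remove unmeasured confounding, so conclusions should be worded as associations.
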